**A Randomized Feasibility Study Evaluating Temozolomide Chronotherapy for High Grade Glioma**

**Protocol Revision History**

Initial Approval Version	05/11/2016
Amendment #1 Version	09/29/2016
Amendment #2 Version	01/27/2017
Amendment #3 Version	08/23/2017
Amendment #4 Version	09/25/2018
Amendment #5 Version	11/09/2018
Amendment #6 Version	09/17/2020
Amendment #7 Version	08/02/2021
Amendment #8 Version	03/22/2022
Amendment #9 Version	09/20/2022

# A Randomized Feasibility Study Evaluating Temozolomide Chronotherapy for High Grade Glioma

## SCHEMA

## Glossary of Abbreviations

AE	Adverse event
CBV	Cerebral Blood Volume
CNS	Central nervous system
CR	Complete response
CRF	Case report form
CT	Computed tomography
CTCAE	Common Terminology Criteria for Adverse Events
DNA	Deoxyribonucleic acid
DOB	Date of Birth
DSM	Data and Safety Monitoring
HRPO	Human Research Protection Office (IRB)
HGG	High Grade Glioma
IRB	Institutional Review Board
MD	Medical Doctor
MLA	Minimal lumen area
MRI	Magnetic resonance imaging
NCI	National Cancer Institute
ORR	Overall response rate
OS	Overall survival
PD	Progressive disease
PFS	Progression Free Survival
PI	Principal investigator
PR	Partial response
QASMC	Quality Assurance and Safety Monitoring Committee
QOL	Quality of Life
RANO	Response Assessment in Neuro-Oncology
SAE	Serious adverse event
SAP	Statistical analysis plan
SD	Stable disease
T2/FLAIR	T2-weighted Fluid Attenuated Inversion Recovery
TEAE	Treatment-emergent adverse events
TMZ	Temozolomide
UPN	Unique patient number
WHO	World Health Organization

[figure not shown]

## 1.0 BACKGROUND AND RATIONALE

### 1.1 Glioblastoma Multiforme

Glioblastoma multiforme (GBM) is the most aggressive and most common malignant primary brain tumor in adults (Ostrom et al., 2013). GBM accounts for 15.6% of all primary brain and central nervous system (CNS) tumors and 54.4% of all gliomas (Ostrom et al., 2013; Central Brain Tumor Registry of the United States) (Figure 1).

[figure not shown]
**Figure 1. Distribution of primary brain and CNS tumors.** (a) Distribution of primary and CNS based on histology. (b) Distribution of primary brain and CNS gliomas based on histology. Ostrom et al., 2013, modified.

Standard therapy for treatment of GBM includes surgical resection followed by radiation

therapy with concomitant temozolomide.

## 1.2 Temozolomide (Temodar)

The addition of the DNA alkylator temozolomide extended median survival by 2.5 months compared to surgical resection and radiation therapy alone (Stupp et al., 2005; figure 2).

[figure not shown]
**Figure 2.** Progression-free survival (PFS) (left) and overall survival (OS) (right) of GBM patients receiving radiotherapy plus temozolomide versus radiotherapy alone. (Stupp et al., 2005, modified).

Despite initial response to standard therapy, GBM has a poor prognosis, resulting in a median survival of 14.6 months (Ohka et al., 2012). Development of new therapies is important, but equally important is the optimization of currently available therapies for patients who are fighting to survive brain tumors now.

## 1.3 Chronotherapy

[figure not shown]
Chronotherapy is the improvement of treatment outcomes by minimizing treatment toxicity and maximizing efficacy through delivery of a medication according to the timing of biological rhythms within a patient (Levi and Okyar, 2011). This concept has been applied to a variety of medications, including chemotherapeutics. Chronochemotherapy has successfully improved anti-tumor effect in the treatment of metastatic colon cancer (Levi et al., 1995, 2001; Innominate et al., 2010), improved survival rate in patients with ovarian cancer (Kobayashi et al., 2002), and decreased relapse rate for children with acute lymphoblastic leukemia (Rivard et al., 1993; Schmeigelow et al., 1997). Chronotherapy has the capacity to improve treatment outcomes for many other cancers, including GBM.

In a mouse model of GBM, we have demonstrated greater anti-tumor efficacy of temozolomide during morning administration. Delivery of temozolomide by oral gavage at 7am showed a trend toward increased length of survival compared to delivery at 7pm (Figure 3).

**Figure 3.** Morning temozolamide (TMZ) treatment lengthens survival. Delivery of TMZ at 7am resulted in a longer median survival than 7pm TMZ delivery (11.2 vs 9.1 weeks,  $p=0.057$ ).

[figure not shown]
In a follow-up study with decreased tumor burden, intracranial GBM tumors shrank at a greater rate following 7am TMZ treatment compared to 7pm TMZ treatment. Tumor size was determined based upon weekly measurement of a bioluminescent reporter expressed by tumor cells. Figure 4 demonstrates a reduction in average tumor size for mice receiving TMZ. Mice receiving vehicle have continued tumor growth.

**Figure 4.** Morning TMZ treatment results in greater reduction in tumor size compared to evening TMZ treatment.

[figure not shown]
#### 1.4 Circadian Clock

For decades, scientists have studied the regulation of daily oscillations in biological processes. At the end of the twentieth century, a regulator of these daily oscillations was discovered within individual cells, known as the molecular clock. Core clock genes form a molecular clock within cells to regulate a variety of cellular processes through the transcriptional control of gene expression (Reppert & Weaver, 2002). Reduced expression of several core clock genes, including Period2 and Period3, has been correlated with decreased survival in glioma patients (Repository for Molecular Brain Neoplasia Data, Figure 5).

**Figure 5. Decreased survival is correlated with reduced core clock gene expression in gliomas.** Downregulated expression of core clock genes Period2 and Period3 is linked to decreased survival in 343 glioma patients (Repository for Molecular Brain Neoplasia Data).

The molecular clock has also been linked to the DNA damage response pathway through protein-protein interactions of Period1 and Period3 with ATM, enhancing downstream phosphorylation of Chk2 in response to DNA double strand breaks (Figure 6; Gery et al., 2006; Im et al., 2010). These discoveries suggest a role for the molecular clock in the cellular response to DNA damage. Therefore, DNA damaging agents like temozolomide may be most effective at the time when core clock proteins Period1 and Period3 are most abundant in the cell.

**Figure 6.** Survival curves of patients with metastatic colorectal cancer according to the presence or absence of circadian disruption before chemotherapy start. The locomotor rhythm, recorded by a wrist-actigraph, was used as circadian biomarker. Circadian disruption was defined as being present in patients whose dichotomy index was in the lowest quartile (dashed grey line). The left panel shows data from 192 patients, receiving chronomodulated chemotherapy, as first or second line treatment. The right panel shows data from 130

previously untreated patients receiving either chronomodulated or conventional chemotherapy. (from Innominate et al, ADDR 2010).

### **1.5 Anti-Tumor T Cell Activity and Circadian Rhythms**

The immune response is an important predictor of glioma progression. Generally, the immune system and, more specifically, T lymphocytes are known to recognize tumor cells and target them for destruction. This action can initially restrain solid tumor growth. In support of this concept, glioma patients with lymphopenia have worse OS (Grossman et al, 2011). Chemotherapy such as TMZ that targets highly proliferative populations affects T cell populations in addition to tumor cells. T lymphocyte populations experience rapid proliferation, especially after exposure to activating antigen, like that released when a tumor cells dies from chemotherapy. However, the rapid proliferation of the T lymphocytes could be inhibited by chemotherapy. Glioma patients given TMZ and radiation experience lymphopenia after two months of treatment and lymphocyte counts remain depressed during the entire course of treatment (Grossman et al 2011). It would be ideal to specifically target the tumor cells while allowing the anti-tumor T cells to remain.

Like many other processes in the body, lymphocyte proliferation is dependent on circadian rhythms. Multiple studies have shown differential effects on lymphopenia depending on the time of day chemotherapy is administered. In a retrospective study, gemcitabine given at 9:00 am was less toxic to lymphocytes than gemcitabine given at 3:00 pm (Iwata K et al, 2011). In other studies, T cell progenitors in the bone marrow were found to be less proliferative at night. Due to the reduced proliferation, nighttime administration of docetaxel and irinotecan was found to reduce lymphocyte toxicity (Tampellini M et al 1998, Ohdo S 1997). This would suggest administering chemotherapy at a time of less T cell proliferation would prevent lymphopenia and potentially support the T cell mediated anti-tumor immune response as well as allow patients to stay on treatment schedule. This could be an addition mechanism by which patients could benefit from chronotherapy.

### **1.6 Quality of Life**

Beyond patient outcome and measured biologic outcomes, it is also important to consider patient quality of life in response to treatment. Quality of life refers to the patient's ability to conduct themselves as normal in reference to physical well-being, social interactions, emotional well-being, and ability to function normally. These qualities can be assessed through surveys administered to the patient throughout their disease and treatment (Piil et al 2015, Omuro et al 2014). Side effects and disease progression can influence quality of life significantly. In this study we will assess quality of life to determine how chronotherapy increases quality life experienced by some patients.

### **1.7 Study Rationale**

Temozolomide (TMZ) is the chemotherapy drug approved by the FDA to increase survival in glioblastoma (GBM) patients beyond surgical resection and radiation therapy alone. Give its activity in astrocytomas, TMZ is commonly used in grade III anaplastic astrocytoma (AA) as well. Both grade III AA and grade IV GBM are high grade gliomas

(HGG). The short half-life of this drug and known oscillations in DNA damage repair make it an ideal candidate for chronotherapy. Chronotherapy has improved outcomes through the reduction of side effects and increase in anti-tumor activity for a variety of cancers, but has never been applied to the treatment of gliomas. Based on the preliminary preclinical data for chronotherapeutic TMZ treatment of intracranial glioma xenografts and the success of chronotherapy in the treatment of other cancers, we hypothesize that the timing of TMZ treatment will alter its efficacy and toxicity.

These effects will be assessed by the following means:

1. Randomized assignment of patients to one of two treatment time frames (before 10:00 versus after 20:00).
2. Measurement of hematologic toxicity throughout treatment.
3. Assessment of QOL through surveys.
4. Correlation of PFS and OS to chronotherapeutic treatment windows.
5. Assessment of daily rest-activity rhythms as well as overall daily activity.

## **2.0 OBJECTIVES**

This exploratory study will collect pilot data for assessment of treatment outcomes in future glioma chronotherapeutic studies.

### **2.1 Primary Objective**

To determine the feasibility of treatment compliance and randomization of HGG patients to receive temozolomide between morning (before 10:00) or evening (after 20:00) treatment groups. Feasibility is defined as at least 80% compliance with assigned administration time.

### **2.2 Secondary Objectives**

1. To determine the number of HGG patients with grade 3 or 4 hematologic toxicity, including lymphopenia, thrombocytopenia, neutropenia and anemia, while receiving temozolomide when administered in the morning (before 10:00) or evening (after 20:00).
2. To assess quality of life using quality of life surveys in HGG patients receiving temozolomide in the morning versus evening.
3. To evaluate progression-free survival of HGG patients taking TMZ in the morning versus evening through chart review or patient visits.
4. To determine overall survival of HGG patients taking TMZ in the morning versus evening through chart review or patient visits.
5. To correlate the sleep-wake cycles of patients receiving temozolomide for treatment of HGG with treatment outcomes for morning versus evening TMZ treatments.

## **3.0 PATIENT SELECTION**

### **3.1 Inclusion Criteria**

1. **Newly diagnosed and recurrent high grade gliomas (WHO grades III & IV) and high risk WHO grade II gliomas who are to begin treatment with monthly high dose temozolomide therapy.**
2. At least 18 years of age.
3. Karnofsky performance status  $\geq 60\%$ , see Appendix A
4. Ability to understand and willingness to sign an IRB approved written informed consent document.

### **3.2 Exclusion Criteria**

1. Pregnant and/or breastfeeding. Women of childbearing potential must have a negative pregnancy test within 14 days of study entry.

### **3.3 Inclusion of Minorities**

Women and members of all races and ethnicities are eligible for this trial.

## **4.0 REGISTRATION PROCEDURES**

**Patients must not start any protocol intervention prior to registration through the Siteman Cancer Center.**

The following steps must be taken before registering patients to this study:

1. Confirmation of patient eligibility
2. Registration of patient in the Siteman Cancer Center OnCore database
3. Assignment of unique patient number (UPN)

### **4.1 Confirmation of Patient Eligibility**

Confirm patient eligibility by collecting the information listed below:

1. Registering MD's name
2. Patient's race, sex, and DOB
3. Three letters (or two letters and a dash) for the patient's initials
4. Copy of signed consent form
5. Completed eligibility checklist, signed and dated by a member of the study team
6. Copy of appropriate source documentation confirming patient eligibility

#### **4.2 Patient Registration in the Siteman Cancer Center OnCore Database**

All patients must be registered through the Siteman Cancer Center OnCore database.

#### **4.3 Assignment of UPN**

Each patient will be identified with a unique patient number (UPN) for this study. All data will be recorded with this identification number on the appropriate CRFs.

#### **4.4 Randomization**

Eligible patients will be randomized on a 1:1 basis to receive temozolomide at one of two time points: before 10:00 or after 20:00. A computer-generated randomization scheme is used to assign subjects. It is maintained centrally by the study statistician.

### **5.0 STUDY PLAN**

#### **5.1 Study Procedures**

Temozolomide will be given as per standard of care. Typical dosing is 150 to 200 mg/m^2 on Days 1 through 5 of a 28-day treatment cycle. Patients will be randomized to take their temozolomide doses in the morning (before 10:00) or evening (after 20:00). Compliance with dosing times will be verified by means of a medication diary (Appendix B). Patients who miss taking their dose at the assigned time will be instructed to take the dose as soon as they can (as long as the next scheduled dose is at least 12 hours away) rather than omitting it.

Patients will be given an ActTrust Condor Instrument watch after signing the consent form. Patients will be required to wear the ActTrust Condor Instrument watch 24 hours per day; it should only be removed at specified data collection time points (see protocol calendar 9.0). Actimetry data will be collected at corresponding time points with the return of the patient to clinic every 8 weeks. The ActTrust watch does not require the patient to charge the device, thus the patient will never have to remove the watch and a new, fully charged, watch will be provided to the patient at every collection time point.

#### **5.2 Study Assessments**

##### **5.2.1 Hematologic toxicity**

Hematologic toxicity will be assessed by standard blood collection. Blood draws will occur within the same 4-hour window each cycle for each patient to take into account peripheral blood T cell numbers. (Timing of draws need not be

synchronized across patients, only consistent for each individual patient.)

Hematologic toxicity will include grade 3 and 4 lymphopenia, thrombocytopenia, anemia and neutropenia. The criteria are summarized in the following chart:

Toxicity	Cell Type	Grade III criteria	Grade IV criteria
Lymphopenia	Lymphocytes	<500-200/mm 	<200/mm 
Leukopenia	Leukocytes	<2000-1000/mm 	<1000/mm 
Neutropenia	Neutrophils	<1000-500/mm 	<500/mm 
Thrombocytopenia	Platelets	<50,000-25,000/mm 	<25,000/mm 
Anemia	RBC (Hemoglobin)	<8.0-6.5 g/dL	<6.5 g/dL

### **5.3 Duration of Study Participation**

Patients will be considered active participants from time of consent through 2 months following the last cycle of temozolomide. Patients will be followed after this time for 24 months.

### **5.4 Definition of Evaluability**

Patients receiving a minimum of one full cycles of TMZ will be evaluable for the primary endpoint.

## **6.0 DOSE DELAYS/DOSE MODIFICATIONS**

Dose delays or dose modifications will follow the standard of care.

## **7.0 CORRELATIVE STUDIES**

### **7.1 Quality of Life Surveys**

Patient quality of life will be assessed using a standard quality of life survey specifically designed for brain cancer patients (the FACT-Br, see Appendix C). QOL assessments will be performed at the following time points:

- baseline
- at the beginning of each cycle of chemotherapy
- 1 month after the final chemotherapy treatment.

The QOL surveys will be administered during an office visit by the study coordinator.

## **7.2 Wrist Actimetry and Sleep Questionnaire**

The ActTrust Condor Instrument watches are wrist actimetry/accelerometers. Large datasets from these devices can be accessed and analyzed through ActStudio (Condor Instruments). This technology has been used already by several groups at Washington University in St. Louis.

Patients will wear an accelerometer on their wrist to measure activity level during the day and at night until two months after the end of treatment. The accelerometer will appear similar to an athletic wristwatch. Patients will be required to wear the accelerometer at all times starting at the beginning of treatment or as soon as they are enrolled in the study, whichever is later. Patients will remove the accelerometer only during situations when the accelerometer would be completely submersed in water or liquid. Wrist actigraphy will be quantified in one-minute bins for the duration of the recording (typically 60 days per patient). The data (counts per minute) will be quantified in terms of average activity per day, percent of activity during waking, percent of activity during sleep, chronotype (average time of daily mid-sleep), chronotype variability (e.g. cycle-to-cycle standard deviation of daily chronotype), sleep duration, nap duration, and number of naps per day. This data will be collected once every 2 months. Patients will not need to charge the watch and upon data collection, a new watch (that is fully charged) will be available for them to take. Once data are collected, it will be analyzed for sleep/wake cycles and overall activity level. Total activity will be measured as average acceleration over 24 hours. Patterns of acceleration will also be noted relative to treatment times in 2 hour increments.

At baseline and at the beginning of each cycle of TMZ, the patient will complete a sleep questionnaire that will be used in conjunction with the ActTrust watch. This qualitative data (sleep questionnaire) will be used with the quantitative data (collected via the ActTrust watch) to assess the level of disruption in sleep/wake cycles experienced by the patient while on study. This data will be collected up to 1 month after the last TMZ treatment. These sleep questionnaires will be administered during an office visit by the study coordinator.

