#### **13.1.2 Secondary Endpoints**

1. Number of patients experiencing lymphopenia, thrombocytopenia, neutropenia and anemia in each group as measured by standard blood draws. Thresholds for each event are listed in the table under Study Assessments below.
2. Score on FACT-BR quality of life survey between morning and evening treatment to quantitatively measure quality of life.
3. Progression-free survival as determined by chart review or patient visit.
4. Overall survival as determined by chart review or patient visit.
5. Correlation between sleep pattern and response to treatment in morning and evening groups.

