## **13.2 Data Analysis**

### **13.2.1 General Considerations**

All data will be evaluated as observed, and no imputation method for missing values will be used. All data will be presented in a descriptive manner. Each cohort will be analyzed separately, and no multiplicity adjustment across cohorts will be

performed. All other analyses are considered as exploratory, even if statistical tests are used.

Descriptive statistics will be used to summarize the trial results, i.e., statistics for continuous variables may include means, medians, ranges and appropriate measures of variability. Qualitative variables will be summarized by counts and percentages. The uncertainty of estimates will be assessed by confidence intervals. Unless otherwise specified, the calculation of proportions will be based on the sample size of the population of interest. Counts of missing observations will be included in the denominator and presented as a separate category if not otherwise specified in the statistical analysis plan (SAP).

Duration of response, according to RANO, will be calculated for each subject and will be analyzed using the Kaplan-Meier method in the primary cohorts separately.

PFS will be presented in subject listings and analyzed using the Kaplan-Meier method in the primary cohorts separately.

Correlation analysis (significance at  $R^2 \geq 0.8$ ) and slope analysis (Fisher's Exact Test) of dependent variables (naps/day, nap duration, sleep duration, % activity during waking, % activity during sleep, chronotype, chronotype variability) and independent variables (tumor grade, time since TMZ administration, time of day of TMZ administration, time since diagnosis date, tumor size, immune health) will be carried out. Each variable will be calculated daily and averaged over the collection period. Daily calculation reveals stability, while the average reveals variability.

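### The sleep–outcome correlation (objective and endpoint 5) sets no cut-off before the outcome, so post-progression actimetry can create or inflate it

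*Combined protocol and SAP*

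**What the plan says.** **Recording window.** Section 7.2 has the watch measure "activity level during the day and at night until two months after the end of treatment". Section 5.3 agrees: "Patients will be considered active participants from time of consent through 2 months following the last cycle of temozolomide". The study calendar (Section 9.0) calls the recording continuous. Nothing stops it at progression. The same Section 7.2 also says activity is quantified "for the duration of the recording (typically 60 days per patient"), which does not fit that window. The sleep questionnaire has its own limit: "This data will be collected up to 1 month after the last TMZ treatment".

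**Use of the data.** Secondary objective 5 (Section 2.2) is "To correlate the sleep-wake cycles of patients receiving temozolomide for treatment of HGG with treatment outcomes for morning versus evening TMZ treatments". Secondary endpoint 5 (Section 13.1.2) is "Correlation between sleep pattern and response to treatment in morning and evening groups".

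**Analysis.** Section 13.2.1 says: "Each variable will be calculated daily and averaged over the collection period". It treats the sleep measures as dependent variables. Its independent variables are tumor grade, time since and time of day of TMZ, time since diagnosis, tumor size and immune health. PFS, OS and response are not among them. It sets significance of a correlation at R² ≥ 0.8.

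**Outcome clock.** PFS runs from the start of treatment (Section 11.3.6) and response is assessed every 8 ± 1 weeks (Section 11.1), so outcomes occur while the watch is recording. No section gives a landmark, a cut at progression or a time-dependent model.

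**The concern.** A variable used to predict an outcome should be measured before that outcome. Here part of the sleep record can follow progression, and how large a part depends on when progression occurs. A patient who progresses early and stops treatment has a short recording, much of it post-progression. A patient who progresses late, or after recording has ended, has little or none. If activity falls with progression, the early progressor's average is lower for that reason alone, and the analysis reads this as disrupted sleep going with poor outcome. The length of the recording itself also depends on the outcome.

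The protocol's own precedent avoids this: Figure 6 (Section 1.4) classifies patients by circadian disruption before chemotherapy starts. What is at stake is the study's stated purpose in Section 2.0, which is to provide pilot data for later glioma chronotherapy studies.

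**Working it through.** The plan gives no effect size, power or precision for this correlation, so there is no figure to reproduce.

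**Step 1. Share of the recording after progression.** Assume treatment stops at progression at month t; Section 6.0 leaves dose changes to standard of care and gives no such rule. Recording then ends at t + 2 months, and the share is 2/(t + 2).

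- t = 2: 2/4 = 50%
- t = 4: 2/6 = 33%
- t = 6: 2/8 = 25%
- Progression after recording has ended: 0%

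With a 1 SD fall in activity, the whole-recording mean drops by 0.50, 0.33, 0.25 and 0 SD respectively.

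**Step 2. Null simulation.**

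- From the documents: 40 patients (Section 13.0), randomized 1:1 (Section 4.4), so 40/2 = 20 per group; 28-day cycles (Section 5.1); recording to two months after treatment, taken as 60 days.
- Assumed: exponential, fully observed PFS with median 6–12 months; treatment to progression or at most 6 or 12 cycles; activity falling by δ = 0.5–1.5 between-patient SD at progression or from 4 weeks before it.
- Recording end = min(PFS, cycles × 28 d) + 60 d.
- Recorded mean = z − δ × (fraction of the recording after onset of the fall), with z independent of PFS.
- Test: Spearman correlation of recorded mean with PFS, two-sided 5%.

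| Analysis | Setting | Positive at nominal 5% |
|---|---|---|
| Whole recording, pooled, n = 40 | all settings (mean correlation 0.10–0.45) | 10%–86% |
| Whole recording, pooled, n = 40 | 1 SD, 8 months | 25%–47% |
| Whole recording, per group, n = 20 | all settings (similar mean correlation) | 7%–51% |
| Whole recording, per group, n = 20 | 1 SD, 8 months | 14%–25% |
| First 60 days only, pooled | 1 SD, 8 months | 11%–24% |
| 8-week landmark, pooled | all settings | 4%–7% |

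A second simulation (n = 40, median PFS 4, 7 or 12 months, shift at progression of 0.5, 1 or 2 SD) gives mean correlations of 0.09–0.13, 0.18–0.26 and 0.33–0.48, with 9%–14%, 20%–39% and 56%–90% positive. With a 2-month landmark it gives 4.8%–5.5%. Using only pre-progression days gives 4.6%–5.3%, but there the change begins exactly at progression. If sleep worsens some weeks earlier, a cut at progression does not remove all of the effect.

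**Step 3. Against the plan's criterion.** R² ≥ 0.8 means |r| ≥ √0.8 = 0.894. No pooled run reached it. A two-sided 5% test at n = 40 needs |r| of about 0.31.

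**Step 4. Patients lost to a landmark.** Under exponential PFS the proportion progressing or dying before day d is 1 − 2^(−d/(30.44 × median)).

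- Week 8 (d = 56): 1 − 2^(−56/182.6) = 19% at a 6-month median; 1 − 2^(−56/365.3) = 10% at 12 months.
- End of week 9 (d = 63): 21% and 11%.

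**The case against.** **Sleep is the dependent variable in Section 13.2.1, and no outcome is listed.** A fall in activity as tumor size increases would be a real association in that analysis. This stands as a limit: the simulated analysis is one reading of the plan. But it leaves the method for objective 5 unspecified rather than protected, and the only summary of the sleep variables that the plan offers is the average over the collection period.

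**The collection period may mean one download.** Data are collected every 8 weeks (Section 5.1) and Section 7.2 mentions 60 days. That is plausible. If only the first 60 days were used, the bias would be smaller but would not vanish (11%–24% pooled at 1 SD and 8 months). No section says that only those days are used.

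**The analysis is by group.** Endpoint 5 refers to morning and evening groups, and Section 13.2.1 analyses cohorts separately. This stands: the per-group rates are the relevant ones and are roughly half the pooled ones. The mean correlation is hardly changed.

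**The plan's threshold is R² ≥ 0.8 and the analysis is exploratory.** Also true. A reader might infer that the trial will declare sleep prognostic because of progression alone. The documents do not support that. The artefact falls far short of the threshold, and at 1 SD and 8 months most simulated trials are negative even at 5%. Estimates with confidence intervals would still be reported, however, and Section 13.2.1 allows for statistical tests.

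**The size comes from assumptions.** The documents do not say how far progression changes activity. Chronotype, naps and sleep duration have no stated direction of change. The wide ranges mostly reflect the assumed shift.

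**Conclusion.** The point holds in limited form. Three facts are in the text: recording runs to two months after treatment, sleep is to be correlated with outcome, and nothing restricts the sleep data to time before the outcome. An analysis that follows the plan can therefore create or inflate a sleep–outcome correlation. The null mean correlation is about 0.1–0.45 across the assumed settings, and the nominal 5% error rate at 1 SD and 8 months becomes about 14%–25% per group or 25%–47% pooled.

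This rests on treatment stopping at progression, on a fall in activity at or shortly before it, and on averaging over the whole recording. It would be too strong to say that progression necessarily produces the correlation, or that the trial's conclusions are compromised: the primary feasibility endpoint is unaffected. The damage is confined to exploratory pilot estimates that a later trial might use. A cheap improvement is worth making.

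**What to change.** Amend the SAP text for objective and endpoint 5; no new data are needed.

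1. Define the sleep predictor as actimetry up to the first 8-week collection.
2. Analyse PFS, OS and response after a landmark, within each arm, among patients alive and progression-free at it. Name the outcomes explicitly, since Section 13.2.1 lists none of them.
3. Because the first scheduled scan falls at 8 ± 1 weeks, set the landmark so that progression on that scan counts as before it, for example at the end of that scan window.
4. Show later actimetry descriptively, split at progression. Add a sensitivity analysis using only pre-progression days, noting that it does not guard against decline that starts before progression is documented.
5. Reconcile the typical 60-day recording in Section 7.2 with recording to two months after treatment.

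The cost is that patients who progress or die before the landmark leave this one analysis: about 10%–20% at median PFS of 12 to 6 months, slightly more if the landmark is at the end of week 9.
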